8.4 Outcome measures for analyses

Independent Central Review of RECIST based assessments

The ICR of all radiological imaging data will be carried out using RECIST version 1.1. All radiological scans for all patients (including those at unscheduled visits, or outside visit windows) will be provided to the ICR. Prior RT reports for patients (at baseline) and information on any lesions that were biopsied to provide a tumor sample for study entry (see Section 5.7.2) will also be provided to allow the selection of appropriate target lesions. The imaging scans will be reviewed by two independent radiologists using RECIST 1.1 criteria and will be adjudicated if required. For each patient, the ICR will define the overall visit response data (CR, PR, SD, PD or not evaluable [NE]) and the relevant scan dates for each time point (ie, for visits where response or progression is/is not identified). If a patient has had a tumor assessment which cannot be evaluated then the patient will be assigned a visit response of NE (unless there is evidence of progression in which case the response will be assigned as PD).

Further details of the ICR will be documented in the Independent Review Charter.

Investigator RECIST based assessments

From the investigators review of the imaging scans, the RECIST tumor response data will be used to determine each patient's visit response according to RECIST version 1.1. At each visit, patients will be programmatically assigned a RECIST 1.1 visit response of CR, PR, SD or PD depending on the status of their disease compared with baseline and previous assessments. If a patient has had a tumor assessment which cannot be evaluated then the patient will be assigned a visit response of NE (unless there is evidence of progression in which case the response will be assigned as PD).

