To achieve 'unequivocal progression' on the basis of NTLs, there must be an overall level of substantial worsening in non-target disease such that, even in presence of stable disease or partial response in TLs, the overall tumour burden has increased sufficiently to merit discontinuation of therapy. A modest 'increase' in the size of 1 or more NTLs is usually not sufficient to qualify for unequivocal progression status.

New lesions

Details of any new lesions will also be recorded with the date of assessment. The presence of one or more new lesions is assessed as progression.

A lesion identified at a follow-up assessment in an anatomical location that was not scanned at baseline is considered a new lesion and will indicate disease progression.

The finding of a new lesion should be unequivocal: ie, not attributable to differences in scanning technique, change in imaging modality or findings thought to represent something other than tumour.

If a new lesion is equivocal, for example because of its small size, the treatment and tumour assessments should be continued until the new lesion has been confirmed. If repeat scans confirm there is a new lesion, then the progression date should be declared using the date of the initial scan.

Symptomatic deterioration

Symptomatic deterioration is not a descriptor of an objective response: it may be a reason for stopping study therapy.

Patients with ‘symptomatic deterioration’ requiring discontinuation of treatment without objective evidence of disease progression at that time should continue to undergo tumour assessments where possible until objective disease progression is observed.

Evaluation of overall visit response

The overall visit response will be derived using the algorithm shown in Table 23.

Target lesions	Non-target lesions	New lesions	Overall response
CR	CR	No	CR
CR	N/A	No	CR
CR	Non CR/Non PD	No	PR
CR	NE	No	PR
PR	Non PD or NE	No	PR
SD	Non PD or NE	No	SD
NE	Non PD or NE	No	NE
PD	Any	Yes or No	PD
Any	PD	Yes or No	PD
Any	Any	Yes	PD

CR Complete Response, PR Partial Response, SD Stable Disease, PD Progressive Disease, NE not evaluable, N/A not applicable (only if relevant if there were no NTL at baseline)

CONFIRMATION OF PROGRESSION

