3.1 Derivation of RECIST visit responses

For all patients, the RECIST tumor response data will be used to determine each patient's visit response according to RECIST version 1.1. It will also be used to determine if and when a patient has progressed in accordance with RECIST and also their best objective response.

Baseline radiological tumor assessments are to be performed no more than 28 days before the start of IPs and ideally as close as possible to the start of IPs. Tumor assessments are then performed every 8 weeks following the first dose of IPs until disease progression. If an unscheduled assessment is performed, and the patient has not progressed, every attempt should be made to perform the subsequent assessments at their scheduled visits. This schedule is to be followed in order to minimise any unintentional bias caused by some patients being assessed at a different frequency than other patients.

An ICR of all radiological imaging data will be carried out using RECIST version 1.1 and the overall visit response will be provided at each visit (i.e. the reviewers will provide the overall visit response according to RECIST 1.1 and no programmatic derivation of visit response is necessary).

From the investigator's review of the imaging scans, the RECIST tumor response data will be used to determine each patient's visit response according to RECIST version 1.1. At each visit, patients will be programmatically assigned a RECIST 1.1 visit response of CR, PR, SD or PD depending on the status of their disease compared with baseline and previous assessments. If a patient has had a tumor assessment which cannot be evaluated then the patient will be assigned a visit response of not evaluable (NE) (unless there is evidence of progression in which case the response will be assigned as PD).

Please refer to sections 3.1.1 and 3.1.2 for the definitions of CR, PR, SD and PD.

RECIST outcomes (ie PFS, ORR etc.) will be calculated programmatically for both the ICR and site investigator data (see section 3.2).

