For calculation of PD and PR for TLs percentage changes from baseline and previous minimum should be rounded to 1 d.p. before assigning a TL response. For example 19.95% should be rounded to 20.0% but 19.94% should be rounded to 19.9%

Missing TL data

For a visit to be evaluable then all TL measurements should be recorded. However, a visit response of PD should still be assigned if any of the following occurred

- A new lesion is recorded
- A NTL visit response of PD is recorded
- The sum of TLs is sufficiently increased to result in a 20% increase, and an absolute increase of ≥ 5 mm, from nadir even assuming the non-recorded TLs have disappeared

Note: the nadir can only be taken from assessments where all the TLs had a LD recorded.

If there is at least one TL measurement missing and a visit response of PD cannot be assigned, the visit response is not evaluable (NE).

Lymph nodes

For lymph nodes, if the size reduces to < 10 mm then these are considered non-pathological. However a size will still be given and this size should still be used to determine the TL visit response as normal. In the special case where all lymph nodes are < 10 mm and all other TLs are 0mm then although the sum may be >0 mm the calculation of TL response should be over-written as a CR.

TL visit responses subsequent to CR

A CR can only be followed by CR, PD or NE. If a CR has occurred then the following rules at the subsequent visits must be applied:

- Step 1: If all lesions meet the CR criteria (i.e. 0mm or < 10 mm for lymph nodes) then response will be set to CR irrespective of whether the criteria for PD of TL is also met i.e. if a lymph node LD increases by 20% but remains < 10 mm.
- Step 2: If some lesion measurements are missing but all other lesions meet the CR criteria (i.e. 0mm or < 10 mm for lymph nodes) then response will be set to NE irrespective of whether, when referencing the sum of TL diameters, the criteria for PD are also met.
- Step 3: If not all lesions meet the CR criteria and the sum of lesions meets the criteria for PD then response will be set to PD
- Step 4: If after steps 1 – 3 a response can still not be determined the response will be set to remain as CR

TL too big to measure

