A lesion identified at a follow up assessment in an anatomical location that was not scanned at baseline is considered a new lesion and will indicate disease progression.

The finding of a new lesion should be unequivocal: i.e. not attributable to differences in scanning technique, change in imaging modality or findings thought to represent something other than tumor.

New lesions will be identified via a Yes/No tick box. The absence and presence of new lesions at each visit should be listed alongside the TL and NTL visit responses.

A new lesion indicates progression so the overall visit response will be PD irrespective of the TL and NTL response.

If the question ‘Any new lesions since baseline’ has not been answered with Yes or No and the new lesion details are blank this is not evidence that no new lesions are present, but should not overtly affect the derivation.

Symptomatic progression is not a descriptor for progression of NTLs: it is a reason for stopping study therapy and will not be included in any assessment of NTLs.

Patients with ‘symptomatic progression’ requiring discontinuation of treatment without objective evidence of disease progression at that time should continue to undergo tumor assessments where possible until objective disease progression is observed.

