3.1.3 Overall visit response

Table 5 defines how the previously defined TL and NTL visit responses will be combined with new lesion information to give an overall visit response for investigator assessments.

Table 5 Overall visit responses

TARGET	NON-TARGET	NEW LESIONS	OVERALL VISIT RESPONSE
CR	CR or NA	No (or NE)	CR
CR	Non-CR/Non-PD or NE	No (or NE)	PR
PR	Non-PD or NE or NA	No (or NE)	PR
SD	Non-PD or NE or NA	No (or NE)	SD
PD	Any	Any	PD
Any	PD	Any	PD
Any	Any	Yes	PD
NE	Non-PD or NE or NA	No (or NE)	NE

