3.2.1 Primary Endpoint

The primary efficacy endpoint variable is Objective Response Rate (ORR), defined as the percentage of patients with objective response according to RECIST 1.1 by ICR using the evaluable for response analysis set (all patients who have received at least 1 dose of IPs and have measurable disease at baseline according to ICR).

The secondary endpoint variable of ORR using the investigators assessment of RECIST and based on the full analysis set will also be analysed.

An additional sensitivity analysis of ORR will be performed using the ICR data summarized using the full analysis set.

ORR will only include patients whose response has been confirmed by a second scan at least 4 weeks after the initial response. A confirmed response of CR/PR means that a response of CR/PR is recorded at 1 visit and confirmed by repeat imaging not less than 4 weeks after the visit when the response was first observed with no evidence of progression between the initial and CR/PR confirmation visit. Data obtained up until progression, or last evaluable assessment in the absence of progression, will be included in the assessment of ORR. Patients who receive a subsequent anti-cancer therapy (note that for this analysis radiotherapy is not considered a subsequent anti-cancer therapy) and then respond will not be included as responders in the ORR (i.e. both visits contributing to a response must be prior to subsequent therapy for the patient to be considered as a responder).

In the case where a patient has two non-consecutive visit responses of PR, then, as long as the time between the 2 visits of PR is greater than 4 weeks and there is no PD between the PR visits, the patient will be defined as a responder. Similarly, if a patient has visit responses of CR, NE, CR, then, as long as the time between the 2 visits of CR is greater than 4 weeks, then a best response of CR will be assigned.

Table 6 below outlines scenarios for the first and subsequent visit responses and the rules that will be followed to determine whether such patients would be counted in the numerator of ORR for the primary analysis and their classification for Best Objective Response (BOR) for the primary analysis. BOR is included as supportive data for the ORR endpoint.

Table 6 Confirmed ORR and BoR criteria

First time point	Second time point	Confirmed Responder for ORR	Best objective response
CR	CR	Yes	CR
CR	PR	Scenario not possible, CR can only be followed by CR PD, NE	SD, PD or PR ^a

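### For investigator assessments, SAP Table 5 allows CR, PR or SD when new-lesion status is unknown: an undeclared extension of protocol Table 23, probably small in effect and simple to correct

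*SAP*

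**What the plan says.** SAP 3.1.2 describes how new disease is captured: "New lesions will be identified via a Yes/No tick box". A recorded new lesion makes the visit PD whatever the target and non-target status. If neither the Yes/No answer nor the lesion details have been entered, the SAP says "this is not evidence that no new lesions are present, but should not overtly affect the derivation".

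SAP 3.1.3, Table 5, combines target, non-target and new-lesion status "to give an overall visit response for investigator assessments". In each row that gives CR, PR or SD, the new-lesion entry is No with NE accepted as an alternative.

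Protocol Appendix F says: "The overall visit response will be derived using the algorithm shown in Table 23". In Table 23 the new-lesion entry in each CR, PR and SD row is No alone.

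SAP section 6, on changes from the protocol, lists only a correction to a symptom-score threshold.

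For the central review, which supplies the primary endpoint, SAP 3.1 says that "the reviewers will provide the overall visit response according to RECIST 1.1 and no programmatic derivation of visit response is necessary".

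**The concern.** A new lesion is enough by itself to turn a visit into PD. The SAP concedes that a blank does not rule one out, yet scores the visit as if it did. Such a visit can start a response. It can also confirm one, because SAP 3.2.1 asks only for a second CR or PR at least 4 weeks later "with no evidence of progression between the initial and CR/PR confirmation visit", and a blank supplies no such evidence. A blank visit can also provide the stable disease that counts toward DCR.

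At stake are the investigator-assessed results: ORR and DCR, the comparison of investigator with ICR response, and the interim futility count, which uses investigator-assessed responders whether confirmed or not.

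**Working it through.** **1. The two algorithms side by side** (protocol Appendix F, Table 23; SAP 3.1.3, Table 5)

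| Target | Non-target | New lesions, protocol | New lesions, SAP | Visit response |
|---|---|---|---|---|
| CR | CR, or none at baseline | No | No or NE | CR |
| CR | neither CR nor PD, or NE | No | No or NE | PR |
| PR | not PD, or NE | No | No or NE | PR |
| SD | not PD, or NE | No | No or NE | SD |
| NE | not PD, or NE | No | No or NE | NE |

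Table 23 does use NE in its non-target column, but nowhere in its new-lesion column.

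**2. Consistency within the SAP**

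- Target measurement missing (3.1.1): NE, unless PD can still be assigned.
- Non-target status NE (Table 5): target CR is lowered to PR.
- New-lesion status NE (Table 5): nothing changes. Target CR with non-target CR remains CR.

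**3. Direction**

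- *ORR, DCR and the interim count.* Compared with setting the visit to NE, the rule turns NE into CR, PR or SD. The denominators do not move: investigator ORR and DCR use the FAS, and the interim uses 20 patients chosen on baseline disease. These results can therefore only rise or stay the same. This takes SAP Table 6 at its word that CR followed by PR cannot occur.
- *PFS and DoR.* For a patient without a later event, an evaluable blank visit moves the censoring date later. For a patient who progresses later, SAP 3.2.2 censors her if two or more assessments were missed beforehand. If NE visits count as missed, which the SAP does not say, scoring the blank visit as evaluable could preserve an event that NE would turn into censoring. DoR inherits both effects, so no direction can be claimed.

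**4. When one visit changes a result**

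- *Confirmed ORR.* Two non-consecutive PR visits more than 4 weeks apart with no PD between them still confirm, so PR, NE, PR remains a response. Status changes only if the patient has no other qualifying pair. One patient is 1/60 = 1.7 percentage points if all 60 are in the FAS.
- *Interim count.* The count changes only if the blank visit is the patient's only response visit. One patient is 1/20 = 5 points.

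**5. The interim limit**

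Inputs are a Beta(1/3, 1/3) prior, 30 or more responders of 100 at the end, and possible stopping below 4 of 20 (protocol 8.2 and 8.5.4). After x of 20, the number of responders Y among the next 80 is beta-binomial with parameters 1/3 + x and 1/3 + 20 − x.

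- x = 3: P(Y ≥ 27) = 0.0457. This reproduces the stated limit of 4.6%.
- x = 4: P(Y ≥ 26) = 0.139.

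One response therefore separates possible stopping from continuing. The binomial chance of exactly 3 of 20, where one extra response would matter, is 19.0%, 24.3%, 20.5% and 7.2% at a true ORR of 10%, 15%, 20% and 30%. These figures describe how sensitive the limit is. They are not probabilities that a blank answer altered the result.

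**6. How many visits there are**

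The protocol assumes a median PFS of 6 months, about 26 weeks, and scans every 8 weeks. With exponential PFS, the chance of passing each interval without an event is q = 2^(−8/26) = 0.808. Expected scans up to progression, capped at k, are (1 − q^k)/(1 − q).

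- k = 4: 2.99 per patient, × 60 = about 180.
- k = 12: 4.80 per patient, × 60 = about 290.

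The documents give no rate of blank answers to apply to these totals.

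**The case against.** Much of the opposing case stands.

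- *Table 23 is silent.* It has no entry for a missing answer, even in its NE row, so it neither forbids a response nor prescribes NE. A reader might infer that the SAP breaches the protocol. The documents support only that the SAP extends Table 23 without saying so.
- *The protocol tolerates some uncertainty.* Table 23 gives PR or SD with non-target status NE, so it does not require all progression to be excluded. That is correct, but it shows NE written where it was meant to be accepted, and even there target CR falls to PR.
- *The general NE rule may not reach this case.* Protocol 8.4 says "If a patient has had a tumor assessment which cannot be evaluated then the patient will be assigned a visit response of NE". A blank box on a readable scan is not clearly such an assessment, and this point does not rely on that sentence.
- *There are safeguards.* Missing data are queried (protocol 9.4) and source data verified (9.2). The interim needs clean datasets (SAP 5). New-lesion status is listed by visit (SAP 3.1.2), and responders on whom investigator and ICR disagree are described (SAP 4.2.7.3). The question is also cumulative from baseline, so a later No is informative about an earlier blank. All this should make residual blanks few, but the SAP rule still governs those that remain.
- *The interim matters little now.* Stopping was optional. The SAP amendment is dated September 2019 and the study was due to end by the third quarter of 2019, so the interim has probably already taken place. A reader might infer that the futility decision was compromised; nothing in the documents shows that any response rested on a blank visit.

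**Conclusion.** The point holds as a minor one, confined to investigator assessments. The SAP states a rule that can credit or confirm a response without new disease having been excluded. It departs from the wording of every response row in Table 23, is not declared in section 6, and is more lenient than the SAP's handling of missing target lesions.

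Three stronger readings are tempting and are not supported:

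- *The primary result is inflated.* It is not. Central reviewers supply the ICR visit responses and Table 5 is not applied to them.
- *Investigator PFS and DoR are flattered.* The direction depends on whether NE visits count as missed, which the SAP leaves open.
- *The effect can be sized from the visit total.* Assuming that 1–2% of answers stay blank gives roughly 2 to 6 visits (180 × 1% to 290 × 2%). The rate has no source in the documents, the total includes progression visits, and most of the rest do not decide a response.

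The effect therefore cannot be estimated from the documents. It is probably small after queries, on the assumption that the query process works as described. Each patient affected is worth at most 1.7 points of investigator ORR at 60 patients, or 5 points at the interim.

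**What to change.** In SAP Table 5, require No for new lesions in every row giving CR, PR or SD. If the answer and the details are both still blank after query, set the visit to NE unless target or non-target PD is present. Delete the closing clause of the SAP 3.1.2 sentence, which tells the programmer to disregard the blank. State in SAP 3.2.2 whether such NE visits count as missed assessments for PFS censoring.

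If the sponsor prefers to keep the present rule, declare it in SAP section 6 and add a sensitivity analysis of the investigator endpoints that treats these visits as NE.

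The cost is a few lines of SAP text and one programming condition. The downside is that a few investigator visits become NE. If the interim has already been run, counting the blank new-lesion answers behind its responders would settle whether it was touched.

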3.1.3 Overall visit response

Table 5 defines how the previously defined TL and NTL visit responses will be combined with new lesion information to give an overall visit response for investigator assessments.

Table 5 Overall visit responses

TARGET	NON-TARGET	NEW LESIONS	OVERALL VISIT RESPONSE
CR	CR or NA	No (or NE)	CR
CR	Non-CR/Non-PD or NE	No (or NE)	PR
PR	Non-PD or NE or NA	No (or NE)	PR
SD	Non-PD or NE or NA	No (or NE)	SD
PD	Any	Any	PD
Any	PD	Any	PD
Any	Any	Yes	PD
NE	Non-PD or NE or NA	No (or NE)	NE

3.2 Efficacy Variables

The endpoints (ORR, DoR, DCR, PFS) will be derived from the overall visit response date and the scan dates. RECIST assessments/scans contributing towards a particular visit may be performed on different dates and the date of progression will be determined based on the earliest of the scan dates of the component that triggered the progression.

Independent Central Review of RECIST based assessments

The ICR of all radiological imaging data will be carried out using RECIST version 1.1. All radiological scans for all patients (including those at unscheduled visits, or outside visit windows) will be provided to the ICR. Prior radiotherapy reports for patients (at baseline) and information on any lesions that were biopsied to provide a tumor sample for study entry will also be provided to allow the selection of appropriate target lesions. The imaging scans will be reviewed by two independent radiologists using RECIST 1.1 criteria and will be adjudicated if required. For each patient, the ICR will define the overall visit response data (CR, PR, SD, PD or NE) and the relevant scan dates for each time point (i.e. for visits where response or progression is/is not identified). If a patient has had a tumor assessment which cannot be evaluated then the patient will be assigned a visit response of not evaluable (NE) (unless there is evidence of progression in which case the response will be assigned as PD).

Results of this independent review will not be communicated to Investigators and the management of patients will be based solely upon the results of the RECIST 1.1 assessment conducted by the Investigator.

Further details of the ICR will be documented in the Independent Review Charter.

Investigator RECIST based assessments

From the investigators review of the imaging scans, the RECIST tumor response data will be used to determine each patient's visit response according to RECIST version 1.1. At each visit, patients will be programmatically assigned a RECIST 1.1 visit response of CR, PR, SD or PD depending on the status of their disease compared with baseline and previous assessments. If a patient has had a tumor assessment which cannot be evaluated then the patient will be assigned a visit response of not evaluable (NE) (unless there is evidence of progression in which case the response will be assigned as PD).

